8.1 Primary endpoint

Incidence of severe aGVHD after transplantation within 100 days.

8.2 Secondary endpoints

Incidence of aGVHD (any grade) in various target organs, overall survival after transplantation, relapse-free survival rate, relapse rate, incidence of severe infections, safety of treatment, and total cost of treatment.

9. Adverse event and severe adverse event

Starting from the date of signing the informed consent form until the last visit, all adverse events will be evaluated and recorded according to the Common Terminology Criteria for Adverse Events version 5.0.

10. Sample size calculation

The incidence rate of severe aGVHD within 100 days of previous adult transplant patients at the IHCAMS was 18% during 1 December 2020 – 31 December 2021. The incidence rate after using the daGOAT model will fall to 8% per the researchers' estimation. Comparison will be performed using a propensity score matching method to select controls at a ratio of 1:3 from the historical cases. To attain a 0.05 significance level and a 0.8 power at a presumed 5% dropout rate, ≥ 102 participants will need to be enrolled, and ≥ 306 historical controls will need to be matched.

11. Statistical analysis

SAS and R statistical analysis software will be used to conduct the statistical analysis tailored to data properties. The propensity score matching method will be used to select controls at a ratio of 1:3 from the historical cases. Efficacy and safety variables will be compared between the two groups of the matched patients. All comparison tests will be two-sided, and statistical significance will be defined as $P < 0.05$ in all the analyses.

12. Ethical review

The study will be conducted in accordance with the Declaration of Helsinki (2013), relevant regulations issued by the government of the People's Republic of China, and additional precautions required by the ethics review committee at the IHCAMS.

Before the study, the investigator will obtain approvals from the ethics review committee at the IHCAMS regarding the study protocol data sheet, informed consent form, subject enrollment form, and other relevant information to be provided to the subject before enrollment. During the study, if there is any amendment to the study protocol data sheet, informed consent form, subject enrollment form, and other relevant information to be provided to the subject before enrollment, renewed approvals shall be obtained from the IHCAMS ethics review committee before continuation of the study.

13. Preservation of research data

All data of this study will be stored at the IHCAMS. Data sharing among the researchers will abide by the regulations of the People's Republic of China regarding desensitization.

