Exclusion criteria	
1. Tandem transplantation or multiple transplantations;2. Patients who are allergic to or cannot tolerate ruxolitinib;3. Mental or other medical conditions that make the patients unable to comply with the research treatment and monitoring requirements;4. Patients who are pregnant or cannot take appropriate contraceptive measures during treatment;5. Patients who are ineligible for the study due to other factors or will bear great risk if participating in the study.
Sample size	The incidence rate of severe aGVHD within 100 days of previous adult transplant patients at the Institute of Hematology & Blood Diseases Hospital, Chinese Academy of Medical Sciences & Peking Union Medical College (IHCAMS) was 18% during 1 December

	2020–31 December 2021. The incidence rate after using the daGOAT model will fall to 8% per the researchers' estimation. Comparison will be performed using a propensity score matching method to select controls at a ratio of 1:3 from the historical cases. To attain a 0.05 significance level and a 0.8 power at a presumed 5% dropout rate, \geq 102 participants will need to be enrolled, and \geq 306 historical controls will need to be matched.
Dosage regimen	
 ➤ Model-predicted high-risk patients: ruxolitinib 5mg bid po until at least day 60 post-transplant and terminated after day 100. If severe hematological signs occur such as when there is severe neutropenia ($<0.1 \times 10^9/L$), ruxolitinib can be used at half dose or discontinued as appropriate, and can continue to be used after hematology recovery. ➤ Model-predicted moderate-risk patients: ruxolitinib 2.5mg bid p po until at least day 60 post-transplant and terminated after day 100. If severe hematological signs occur such as when there is severe neutropenia ($<0.1 \times 10^9/L$), ruxolitinib can be used at half dose or discontinued as appropriate, and can continue to be used after hematology recovery. ➤ Model-predicted low risk: regular aGVHD prophylactic regimens.
Study endpoints	
Primary endpoint: incidence of severe aGVHD after transplantation within 100 days.
 
Secondary endpoints: incidence of aGVHD (any grade) in various target organs, overall survival after transplantation, relapse-free survival rate, relapse rate, incidence of severe infections, safety of treatment, and total cost of treatment.

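### For 18% vs 8%, 102 participants and 306 controls do not give a 0.05 level and 0.8 power together: power after dropout is about 70% (chi-square) or 68% (Fisher)

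*Protocol*

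**What the plan says.** Section 10 takes the control rate from the centre's own experience: "severe aGVHD within 100 days of previous adult transplant patients at the IHCAMS was 18% during 1 December 2020" to the end of 2021. For the trial group it assumes that "The incidence rate after using the daGOAT model will fall to 8% per the researchers' estimation". Controls are chosen by propensity score matching, three per participant. From these inputs it concludes that at least 102 participants and at least 306 controls suffice "To attain a 0.05 significance level and a 0.8 power at a presumed 5% dropout rate". The Abstract repeats the statement.

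Section 11 adds that "All comparison tests will be two-sided", with significance at P < 0.05. The protocol names neither the variance formula behind the 102 nor the test for the primary endpoint.

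**The concern.** Section 10 promises two properties at once for one sample size: a level and a power. Common two-proportion formulas agree closely when the groups are equal in size, but not at 1:3 when the lower rate is in the smaller group. In that setting the unpooled variance is clearly smaller than the pooled variance that applies when the two rates are equal. A sample size from the unpooled formula then comes out low for any test that holds its level.

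If the planned effect is real, the chance of missing it would be about 30% (chi-square) or 32% (Fisher) instead of the 20% that the protocol implies. The choice of test could also decide the conclusion. With 10/97 events in the trial group (10.3%) and 52/291 in the controls (17.9%), the unpooled z test gives P = 0.048, chi-square 0.078 and Fisher 0.081. A study with historical controls is poorly placed to defend a positive result that depends on the liberal test.

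**Working it through.** **Inputs, all from sections 10 and 11.** Trial rate 0.08; control rate 0.18; 1:3; two-sided 0.05 (z = 1.960); power 0.80 (z = 0.842); dropout 5%. Assumption: independent groups.

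**1. Reproducing 102/306.** Unpooled variance term: 0.08 × 0.92 + 0.18 × 0.82/3 = 0.0736 + 0.0492 = 0.1228.

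n = (1.960 + 0.842)² × 0.1228 / 0.10² = 96.38. Then 96.38/0.95 = 101.46, rounded up to 102, and 102 × 3 = 306. The protocol's figures are reproduced exactly.

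**2. The pooled formula on the same inputs.** Mean rate = (0.08 + 3 × 0.18)/4 = 0.155. Null variance term: 0.155 × 0.845 × 4/3 = 0.1746, against 0.1228 above.

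n = [1.960 × √0.1746 + 0.842 × √0.1228]² / 0.10² = 124.10. Then 124.10/0.95 = 130.63, rounded up to 131, with 393 controls.

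**3. Formula power after dropout.** 102 × 0.95 = 96.9 and 306 × 0.95 = 290.7, so 97 vs 291. The standard errors are √(0.1228/97) = 0.0356 (unpooled) and √(0.1746/97) = 0.0424 (pooled).
- Unpooled: Φ(0.10/0.0356 − 1.960) = Φ(0.85) = 0.802.
- Pooled: Φ((0.10 − 1.960 × 0.0424)/0.0356) = Φ(0.47) = 0.682.

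**4. Exact enumeration of both binomials.** Power is for 18% vs 8%. The level is the two-sided rejection rate at 97 vs 291 when both groups share a rate between 8% and 18%.

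| Test | Power, 97 vs 291 | Actual level, 97 vs 291 | Power, 102 vs 306 |
|---|---|---|---|
| Chi-square | 69.6% | 4.9-5.0% | 71.8% |
| Fisher | 67.8% | 3.9-4.2% | 70.7% |
| Likelihood ratio | 73.1% | 5.0-5.4% | 75.0% |
| Arcsine | 74.4% | 5.2-5.5% | 76.4% |
| Unpooled z at 1.96 | 78.7% | 5.5-5.9% | 80.5% |

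In the direction of benefit, the unpooled z test at 97 vs 291 rejects 3.6-4.5% of the time, against a nominal 2.5%. At 102 vs 306 its two-sided level is 5.5-6.0%.

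**5. Unpooled z with its cut-off raised to hold 5%.** At 97 vs 291, power is 76.4% if the level is held for common rates of 8-20% (cut-off 2.054). It is 71.6% if the level is held for 5-30% (cut-off 2.170). At 102 vs 306 the corresponding powers are 76.9% and 74.0%.

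**6. Where 80% is reached.** At 97 vs 291 and a control rate of 18%, power is 80% at a trial rate of about 7.0% (chi-square) or 6.8% (Fisher). For 18% vs 8%, the smallest evaluable trial group by exact calculation is 122 for chi-square (122/0.95 gives 129 enrolled, 387 controls) and 125 for Fisher (132 enrolled, 396 controls).

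**The case against.** The strongest reply is that 102/306 is not an error: a standard two-sided formula returns it exactly from the stated inputs. That stands, and a reader who infers a miscalculation from the pooled figure of 131 would be wrong. What fails is the claim made for the number, that the level and the power are both attained.

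A second reply is that the 70% depends on a test the protocol does not name, and that a statistical analysis plan may name it. Leaving the test to that plan is no fault, and the figure does vary with the test. But no choice among the tests tried rescues the sentence: those at or near 5% fall short of 80%, and the one that comes close exceeds 5%.

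A third reply is that the unpooled test misses only narrowly, by 1.3 points of power after dropout and less than 1 point of two-sided level. That is fair as to size. The excess is larger in the direction of benefit, however, and once the cut-off is raised to hold 5% the power drops to 72-76%. The likelihood ratio and arcsine tests also run slightly above 5%, so the line is one of degree; neither reaches 80% in any case.

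A fourth reply is that matching may induce correlation within sets and so raise power. This is possible. The pooled-formula power of 0.682 becomes 0.707 at a correlation of 0.05, 0.733 at 0.10 and 0.787 at 0.20; about 0.22 is needed for 0.80. The documents give no value, and the formula that yields 102 ignores correlation too.

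Finally, a reader might conclude that 30 more participants must be enrolled. The finding does not require that. A study may accept lower power if it states it correctly.

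**Conclusion.** Wrong as written. Under the protocol's own rates, allocation and dropout, the sample size delivers about 70% power with chi-square or 68% with Fisher, roughly 10 to 12 points below the stated 80%. Without any dropout the shortfall is still 8 to 9 points. The unpooled z test at 1.96 comes near 80% only by running above the stated level. The conclusion takes 18% and 8% as given, rests on independent groups, and covers the tests listed; it says nothing about whether those rates are realistic.

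**What to change.** Keep 102/306 and correct the power statement in section 10 and in the Abstract, for example:

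*With 102 participants and 306 controls (97 and 291 after 5% dropout), power for 18% vs 8% at two-sided 0.05 is about 70% with a chi-square test (68% with Fisher's exact test), assuming independent groups; 80% power is reached if the trial rate is about 7% or lower.*

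Do not test the primary endpoint with the unpooled z test at 1.96. If the sponsor expects a gain in power from matching, the assumed within-set correlation should be stated with its source.

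The cost is wording in two places. For information only: 80% power at 18% vs 8% would need about 129-132 enrolled with 387-396 controls, depending on the test. That is 27-30 more participants and 81-90 more controls, which is not a cheap change and is not asked for here.

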Safety evaluation	Encompassing physical examination, vital signs, adverse events, concomitant therapy, and abnormal results of laboratory tests.
Statistical analysis	SAS and R statistical analysis software will be used to conduct the statistical analysis tailored to data properties. The propensity score matching method will be used to select controls at a ratio of 1:3 from the historical cases. Efficacy and safety variables will be compared between the two groups of the matched patients. All comparison tests will be two-sided, and statistical significance will be defined as $P < 0.05$ in all the analyses.

2. Research background

At present, there are about 40,000 new allogeneic hematopoietic stem cell transplantation (allo-HSCT) cases every year in the world ^[1, 2], among which about a quarter occur in China. Allo-HSCT has become the primary treatment method for some hematological diseases such as refractory and relapsed acute leukemia and bone marrow failure. The individuals are affected by dynamic and static multi-dimensional parameters as well as post-transplant immune reconstitution. The use of machine learning to integrate big data for predicting severe aGVHD (grade III–IV) may provide a new path towards understanding immune complications after transplantation.

Previous foundation of research

The researchers have compiled the postoperative clinical data of the patients who received HLA-mismatched allogeneic hematopoietic stem cell transplantation (allo-HSCT) at the IHCAMS from 2012 to 2021—named the ‘aGOAT dataset’, which contained 194 dynamic variables of 584 adult patients and 159 dynamic variables of 45 pediatric patients, including complete blood counts, blood biochemistry, electrolytes, cytokines, flow cytometry, antibody, fluid inflow/outflow, and vital signs. Severe aGVHD occurred within 100 days in 16% of the adult patients and 24% of the pediatric patients. A dynamic forecasting model for severe aGVHD, termed the ‘daGOAT model’, was constructed, achieving an AUROC score of more than 0.78. This result has been published in *Nature Computational Science* in 2022.^[3]

This study aims to prospectively evaluate the use of the daGOAT model in real-world clinical settings at the IHCAMS.

1. Gratwohl, A., et al., *One million haemopoietic stem-cell transplants: a retrospective observational study*. *Lancet Haematol*, 2015. 2(3): p. e91-100.

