2. Xu, L.P., et al., *A review of hematopoietic cell transplantation in China: data and trends during 2008-2016*. *Bone Marrow Transplant*, 2017. 52(11): p. 1512-1518.
3. Liu, X., et al. *Dynamic forecasting of severe acute graft-versus-host disease after transplantation*. *Nat Comput Sci* , 2022.2: p. 153-159.

3. Study objective

To evaluate the efficacy and safety of ruxolitinib for prophylactic therapy of adult patients who are predicted to have a high risk for developing severe aGVHD according to the daGOAT model.

4. Study design

This is a prospective single-arm historical-control clinical trial. Adult patients receiving HLA-mismatched allogeneic hematopoietic stem cell transplantation (allo-HSCT) at the IHCAMS will be enrolled after October 1, 2022. The propensity score matching method will be used to select controls at a ratio of 1:3 from the historical cases.

The daGOAT model will dynamically predict the risk for severe aGVHD daily from day 17 to day 23 after transplantation, and medication will be adjusted according to the predicted risk.

The study flowchart is shown in Figure 1 (LR, low risk; MR, moderate risk; HR, high risk).

[figure not shown]

Figure 1. Study flowchart

5. Study population

Adult patients receiving HLA-mismatched allo-HSCT from the IHCAMS.

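### Is the 80% power in section 10 undermined because the historical controls are not tied to the period behind the 18% planning rate?

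*Protocol*

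**What the plan says.** Section 10 (repeated in the abstract) states that the 100-day rate among "previous adult transplant patients at the IHCAMS was 18% during 1 December 2020" to the end of December 2021, expects 8% with the model in use, and will "select controls at a ratio of 1:3 from the historical cases". For two-sided 0.05, 80% power and 5% dropout it asks for at least 102 participants, and at least "306 historical controls will need to be matched".

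Sections 4 and 11 use the same expression for the control source. None of these places gives calendar dates, an eligibility rule or a number available. Section 4 adds that patients "at the IHCAMS will be enrolled after October 1, 2022".

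Section 2 describes another body of historical data: "patients who received HLA-mismatched allogeneic hematopoietic stem cell transplantation (allo-HSCT) at the IHCAMS from 2012 to 2021", "which contained 194 dynamic variables of 584 adult patients and 159 dynamic variables of 45 pediatric patients". There, "Severe aGVHD occurred within 100 days in 16% of the adult patients and 24% of the pediatric patients". The section presents this as the dataset compiled for building the daGOAT model. It does not call it the source of controls.

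**The concern.** In a single-arm trial with matched historical controls, the controls are half of the primary comparison. The planning rate comes from a dated 13-month window, while the controls come from an undated pool. The only adult cohort with a stated size has a lower rate, 16%, and reaches back to 2012.

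Two things would be at stake if that cohort were the pool. First, with a control rate below 18% and the treated rate still at 8%, the trial would have less power than stated. Second, controls could precede the treated patients by up to a decade, so that changes in practice over time would be mixed with the effect of the intervention. There is also a question of supply: 306 controls from 13 months means 306/13 = 23.5 eligible patients a month.

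**Working it through.** **Reproducing the plan's figure.** The inputs from sections 10 and 11 are a control rate of 0.18, a treated rate of 0.08, three controls per treated patient, two-sided 0.05, power 0.80 and dropout 5%. The protocol names no formula. The two-proportion formula with unpooled variance gives

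n = (1.960 + 0.842)² × [0.08 × 0.92 + 0.18 × 0.82/3] / 0.10² = 96.4 treated.

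Then 96.4/0.95 = 101.5, rounded up to 102, and 3 × 102 = 306. Both stated numbers are matched exactly.

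**Is 18% at odds with 16%?** Sixteen percent of 584 is about 93 events. The Wilson 95% interval for 93/584 is 13.2% to 19.1%, which contains 18%. The two figures also describe different groups: section 2 is restricted to HLA-mismatched transplants over ten years, whereas the 18% is described only as adult transplant patients over 13 months. Neither is the rate after propensity matching, which is the one that will apply.

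**Power on both sides of 18%.** After 5% dropout, 102 × 0.95 ≈ 97 treated, with 3 × 97 = 291 controls. Exact binomial enumeration of the unpooled test at two-sided 0.05 gives:

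| Control rate | Treated 8% | Same relative reduction (×8/18) |
|---|---|---|
| 16% | 64% | 74% (treated 7.1%) |
| 17% | 72% | 77% (treated 7.6%) |
| 18% | 79% | 79% (treated 8%) |
| 19% | 84% | 81% (treated 8.4%) |

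At a 16% control rate with the planned 10-point drop (treated 6%), power is 85%. At 16%, the planned power is kept if the treated rate is about 6.7%, a relative reduction of 1 − 0.067/0.16 = 58%, against the planned 1 − 0.08/0.18 = 56%. The 64% arises only if the control rate falls to 16% and the treated rate does not move with it.

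**Supply of controls.** The protocol gives no count for the 13 months. If the 584 adults were spread evenly over 120 months (an assumption), the window would hold 584/120 × 13 = 63. At twice that accrual it would hold about 127. To hold 306, it would need 306/584 = 52% of the cohort, or nearly five times even accrual. All of this assumes that the modelling dataset contains every eligible transplant, which the protocol does not say. Nor does the protocol confine the pool to those 13 months: January to September 2022, before enrolment opened, could also supply controls. The arithmetic shows that the source is unstated, not that 306 is out of reach.

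**Cost of a narrow window.** At 18% versus 8%, the 95% half-width of the difference is 1.96 × √(0.08 × 0.92/97 + 0.18 × 0.82/291) = 7.0 points. With 63 recent controls in place of 291 it is 10.9 points. A wider calendar span buys precision at the price of older controls, which is the ordinary trade-off of this design.

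**The case for a change.** The strongest argument for acting is that the control population is more basic than calipers or matching variables. Section 10 itself asserts 80% power and a required count, so it might be expected to identify the group to which both apply. The historical outcomes are already known, and an undated pool leaves room to choose the period after seeing them. One point in the control rate also matters: with treated at 8%, power falls from 79% to 72% when the control rate goes from 18% to 17%.

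It stands that the protocol is silent on the window, eligibility and size of the pool, and that these ought to be on record before the comparison is made. It does not stand that a stated figure or rule is wrong. Section 10 names earlier adult patients at the centre and, two sentences later, the historical cases. Reading these as the same source is natural, and nothing in the text contradicts it. The case for lost power needs the 584-patient cohort as the pool, a 16% rate surviving the matching, and a treated rate that stays at 8%. None of these is documented. Confounding with calendar time applies to historical-control designs generally, this protocol declares its design openly, and the direction of any bias here is unknown.

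**Conclusion.** No change to the plan follows. The sample size is correct for its stated assumptions, and the 18% is not shown to be wrong. Across control rates of 16% to 19% with treated at 8%, exact power runs from about 64% to 84%. With the planned relative reduction it runs from 74% to 81%. A shortfall is possible, but nothing in the protocol makes it the expected result.

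What is left is missing detail about which patients form the control pool. Analysts must settle that before any matching can be done, and a statistical analysis plan may already do so. Writing it down would clarify section 10 but would add no participants and correct no stated number. This conclusion assumes the unpooled test that reproduces 102 and 306, and 97 and 291 evaluable patients after dropout.

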7.3. Laboratory tests

Laboratory tests performed at diagnosis and before and after transplantation at various time points.

- 1) Blood routine: Red blood cell count, hemoglobin, platelet count, white blood cell count, white blood cell classification count, etc.
- 2) Urine routine: specific gravity, pH, urine sugar, urine protein, urobilinogen, ketone bodies, microscopic red blood cells, urine white blood cells, bacteria, crystals, tube type, etc.
- 3) Coagulation function tests: activated partial thromboplastin time, plasma prothrombin time, international normalized ratio of prothrombin time, thrombin time, plasma fibrinogen, and plasma D-dimer.
- 4) Bone marrow:
 - Smear or biopsy analysis;
 - Immunophenotype analysis by flow cytometry;
 - Chromosome karyotype;
 - Gene mutation analysis.

5) Blood biochemistry.

- Electrolyte includes sodium, potassium, chlorine, calcium and phosphorus, etc.
- Liver function tests include alanine aminotransferase, aspartate aminotransferase, alkaline phosphatase, γ -glutamyltransferase, lactate dehydrogenase, total protein, albumin, total bilirubin, direct bilirubin, total cholesterol, triglyceride, etc.
- Renal function tests include blood urea nitrogen, uric acid and creatinine, etc.

6) Immune cell subset analysis by flow cytometry.

7.4. Other examinations.

- 1) 12-lead electrocardiogram;
- 2) Chest computed tomography;
- 3) Abdominal ultrasound and abdominal CT when necessary;
- 4) Echocardiography when necessary.
- 5) Other examinations that the investigators consider appropriate.

7.5. Follow-up.

Patients will be followed up at days 14, 28, 42, 60, 90, 180, 270, 360 and 540 after transplantation; data on infection, relapse, survival, and quality of life will be collected.

8. Study endpoints

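### Section 11 tests safety variables, adverse events among them, against historical controls, although the only adverse event recording the protocol describes starts at trial consent, which controls never gave

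*Protocol*

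**What the plan says.** - **The comparison.** Protocol Section 11 and the statistical row of the abstract (Section 1) say: "Efficacy and safety variables will be compared between the two groups of the matched patients". The next sentence sets the rule for inference: "All comparison tests will be two-sided, and statistical significance will be defined as $P < 0.05$ in all the analyses".
- **What counts as safety.** The safety evaluation row of the abstract reads: "Encompassing physical examination, vital signs, adverse events, concomitant therapy, and abnormal results of laboratory tests". Section 8.2 makes safety of treatment a secondary endpoint, and Section 3 puts safety in the study objective.
- **How adverse events are obtained.** Section 9 gives the only rule: "Starting from the date of signing the informed consent form until the last visit, all adverse events will be evaluated and recorded", graded by CTCAE version 5.0.
- **Who the two groups are.** Trial patients sign consent (Section 5.1), are enrolled after October 1, 2022 (Section 4) and have scheduled visits from day 14 to day 540 (Section 7.5). Controls are historical cases matched 1:3. The protocol states no adverse event source, grading or time window for them.

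**The concern.** The comparison in Section 11 and the recording rule in Section 9 do not fit together. One calls for a tested comparison of safety variables across the two groups. The other defines adverse event data that can exist in only one of them, because the recording clock starts at a signature that controls never gave.

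Propensity matching balances measured baseline characteristics. It does nothing about how thoroughly outcomes were looked for afterwards. A significant difference in Section 9 events could therefore reflect the treatment, the recording, or both, and the P-value could not say which. Safety is half of the stated objective, so this comparison would be read as evidence.

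**Working it through.** **1. Group sizes.** The protocol's 102 and 306 reproduce from its own inputs (8% vs 18%, 1:3, two-sided 0.05, power 0.80) with the unpooled variance formula:

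n = (1.960 + 0.842)² × [0.08 × 0.92 + 0.18 × 0.82 / 3] / 0.10² = 96.4

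96.4 / 0.95 = 101.5, rounded up to 102, and 3 × 102 = 306.

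The illustration below uses 97 and 291, that is 0.95 × 102 = 96.9 and 0.95 × 306 = 290.7. Taking 5% off the retrospectively matched controls as well is a convenience that Section 10 does not call for. It changes little (step 6).

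**2. Assumptions.** The protocol gives no adverse event rate and no capture rate, so every rate here is assumed. Let p be the true event rate, equal in both groups, and c the share of control events that was recorded. Trial capture is taken as complete. The test then compares p with c × p. Rejection probabilities come from exact enumeration of two independent binomials with a pooled two-proportion z-test, two-sided 0.05, ignoring the matching.

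**3. False significance with no true difference**

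| True rate p | c = 0.9 | c = 0.8 | c = 0.7 |
|---|---|---|---|
| 10% | 0.067 | 0.108 | 0.176 |
| 30% | 0.093 | 0.223 | 0.441 |
| 60% | 0.174 | 0.536 | 0.870 |

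For example, p = 30% and c = 0.8 compares a recorded 30% with 0.8 × 30% = 24%. The test rejects with probability 0.223, of which 0.222 is against the trial arm.

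**4. Direction.** With the assumption reversed (trial arm captured at 0.8, controls fully, p = 30%), the test rejects with probability 0.198, of which 0.197 is against the controls. The direction follows from the assumption, not from the protocol.

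**5. Same record review in both groups**

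- Equal capture of 80% in each group at p = 30%: rejection probability 0.050.
- Price in power for a true 45% vs 30%: 0.767 with full capture, 0.701 at 90%, 0.628 at 80%, 0.552 at 70%.
- Unequal capture despite the same source, at p = 30%: 90% in trial charts vs 80% in control charts gives 0.096, and 95% vs 80% gives 0.150.

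**6. Sensitivity to group size.** With 102 and 306, p = 30% and c = 0.8 gives 0.232. Power for 45% vs 30% falls from 0.785 to 0.647 at 80% capture in both groups.

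**The case against.** **This belongs in the SAP.** Section 11 is short, does not list the safety variables to be tested, and does not say in so many words that Section 9 events are the data for the test. An unseen SAP may choose the variables and set extraction rules for controls, and nothing in the protocol forbids reviewing control charts from the same hospital with CTCAE grading and a common day window. This lowers certainty about what will be done. It does not remove the point: the protocol commits to the comparison, counts adverse events as safety, and provides one recording rule that cannot apply to controls. Grading control charts in retrospect and setting them against prospective trial records would keep the imbalance.

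**A reader might extend the point to laboratory tests, severe infection and relapse.** Section 7.3 has laboratory tests done "Laboratory tests performed at diagnosis and before and after transplantation at various time points", and in Section 7.5 visit-based "data on infection, relapse, survival, and quality of life will be collected". The documents do not support going that far. Section 2 describes a same-hospital dataset for 2012 to 2021 with blood counts, biochemistry, electrolytes and vital signs in 584 adults, and the December 2020 to December 2021 reference period of Section 10 lies within those years. The protocol does not say that controls come from that dataset, so equal capture is not proven, but routine data of this kind evidently exist for historical patients. Section 8.2 also lists relapse rate and severe infections as endpoints separate from safety of treatment.

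**The figures are assumptions.** That is so. They show what unequal recording can do, not what it will do here.

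**Conclusion.** The point holds for adverse events recorded under Section 9. Tested against historical controls as Section 11 is written, they would mix treatment effect with recording intensity, and matching cannot separate the two.

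The size is unknown. Under assumed true rates of 10% to 60% and control capture of 70% to 90%, with full capture in the trial arm, false significance is about 7% to 87% instead of 5%. For rare or well-documented events it may be small.

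Two stronger conclusions should not be drawn:
- **That the trial arm will look less safe than it is.** Under-recording in controls is plausible, but the protocol gives no capture rates and the reverse case gives a similar error the other way.
- **That the main result is compromised.** The primary endpoint and the sample size do not depend on Section 9 and are unaffected.

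**What to change.** Add one or two sentences to Section 11:

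- Adverse events collected under Section 9 are reported descriptively for trial patients, without a test against controls.
- Between-group safety tests are limited to outcomes taken in both groups from the hospital record with the same source, definition and post-transplant day window, for example routine laboratory abnormalities and death.

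The cost is the record extraction for the chosen outcomes in about 102 trial patients and 306 controls. There will be no P-value against controls for other adverse events. Where records miss events, power falls (77% to 63% in the 45% vs 30% example at 80% capture in both groups).

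A common source does not guarantee equal capture. If trial patients' charts are fuller because of the scheduled visits, some bias remains (9.6% instead of 5% at an assumed 90% vs 80%). The protocol should state this as a limitation.
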